Statistical Analysis Plan (Final, Version 1.2)

Principal Investigator: [name]

Research Institution: Sir Run Run Shaw Hospital, Zhejiang University

Register Number: NCT06204497

Date: 2025-10-26

Version: 1.2

Statistical Analysis Plan Authors: [name]

Department of Epidemiology and Biostatistics, Zhejiang University

School of Medicine, China

E-mail: [contact]

1. Introduction

This trial is a multicenter, prospective, randomized, controlled, open label, parallel-group, non-inferiority trial to evaluate the safety and efficacy of stent-based diverting technique (SDT) versus ileostomy in rectal cancer patients. In this trial, SDT is considered to reduce the overall length of post-operation hospital stay and medical costs, improve patients' quality of life, while not increasing the peri-operative complication rate. The primary outcome was the 90-day incidence of severe complications (Clavien-Dindo grade \geq III). Secondary outcomes included overall complication rate, anastomotic leakage rate (grade B/C), length of postoperative hospital stay, hospitalization costs, and 90-day postoperative quality of life.

Patients were randomized 1:1 to two groups:

- SDT group: rectal cancer surgery plus stent-based diverting technique
- Ileostomy group: rectal cancer surgery plus protective ileostomy

Follow-up concluded 90 days after the last patient underwent surgery.

2. Population

● 2.1 Intent-to-treat population

The intent-to-treat (ITT) population will include all randomized participants, with grouping according to their originally assigned treatment,

regardless of whether the allocated intervention was actually received or completed. Primary and secondary outcome analyses will be performed in the intent-to-treat (ITT) population. As randomization was performed intraoperatively, a modified ITT (mITT) population was not defined in this study.

- **2.2 Per-protocol population**

The per-protocol (PP) population includes all randomized participants who completed the study as planned, with no major protocol violations, adequate adherence to the assigned intervention, and sufficient follow-up data for the primary outcome assessment. Primary and secondary outcome analyses will be conducted in the PP population as sensitivity analyses.

- **2.3 As-treated population**

The as-treated (AT) population comprises all randomized patients who actually received the intervention to which they were assigned, regardless of their original randomization group. In this trial, participants randomized to the SDT group but who ultimately underwent ileostomy for various reasons were included in the ileostomy group in the as-treated analysis, and vice versa. All as-treated analyses were conducted as sensitivity analyses.

- **2.4 Safety population**

The safety population comprises all randomized patients in this trial, except those who withdrew prior to surgery. Patients were categorized

based on the treatment actually received, on which safety monitoring was performed. As this is a surgical study with the primary outcome focused on perioperative complications, all eligible patients were included in the safety population. Adverse events were monitored and reviewed by the Data Safety and Monitoring Board (DSMB).

3. Data Management

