4.1 Timing of Analysis

The final statistical analysis will be performed after database lock, which will occur after all patients have completed the 90-day follow-up and all data have been verified, cleaned, and resolved with no outstanding queries. There were no planned interim analyses for the primary outcome in this trial.

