4.6 Primary outcome

The primary endpoint will be analyzed in the ITT population and defined as the rate of severe complications (Clavien-Dindo grade \geq III) within 90 days post-surgery, the primary endpoint will be assessed as follows (Time Frame: For the Study Group, from the SDT to 90 days after surgery; if the patient undergoes ileostomy as a salvage procedure, the time frame will be extended to 90 days after stoma reversal. For the Control Group, from ileostomy creation to 90 days after stoma reversal. For patients in

both groups who do not undergo stoma reversal, the time frame will be defined as 90 days after the initial surgery).

The primary non-inferiority analysis will be based on the risk difference (RD) with a predefined non-inferiority margin of 2.8%. The RD and its 97.5% one-sided confidence interval will be estimated using binomial regression with identity link. For the relative risk (RR), binomial regression with log link will be used to estimate the RR and two-sided 95% confidence interval. The RR is reported as a supplementary effect measure and will not be used for the non-inferiority test ((see appendix Table 2).

Non-inferiority margin justification: The non-inferiority margin of 2.8% was determined based on clinical relevance and pilot data. This margin was defined such that the severe complication rate in the SDT group would not exceed 120% of that in the ileostomy group (i.e., a 20% relative increase). Given the expected severe complication rate of 14% in the ileostomy group in our pilot study, the absolute non-inferiority margin was calculated as $14\% \times 0.2 = 2.8\%$. In clinical practice, an absolute increase of no more than 2.8% in severe complications is considered acceptable, as it is negligible compared with the substantial benefits of SDT: avoidance of stoma creation and reversal, shorter hospital stay, lower medical costs, and improved quality of life.

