Number of high-risk factors, No. (%)		
Single	XX (XX)	XX (XX)
Multiple	XX (XX)	XX (XX)
Pathological TNM stage, No. (%)		
0	XX (XX)	XX (XX)
I	XX (XX)	XX (XX)
II	XX (XX)	XX (XX)
III	XX (XX)	XX (XX)

Table 2

Outcomes	Stent-based Diverting Technique (n=)	Ileostomy (n=)	P value
Primary outcome			
Events (severe complications), No	XX	XX	
Incidence of severe complications, % (95% CI)*	XX (95% CI, XX– XX)	XX (95% CI, XX– XX)	
Between-group difference in incidence, % (97.5% CI)	-XX (–∞, XX%)	-	XX
Relative ratio, % (95% CI)*	XX (XX–XX)	-	XX
Secondary outcomes			
Incidence of total complications, No. (%)*	XX (XX)	XX (XX)	XX
Incidence of mild complications, No. (%)*	XX (XX)	XX (XX)	XX
Complications (Events)	XX (XX)	XX (XX)	-
General complications, No. (%)	XX (XX)	XX (XX)	-
Anastomotic leakage (Grade B)	XX (XX)	XX (XX)	XX
Anastomotic leakage (Grade C)	XX (XX)	XX (XX)	XX
Anastomotic stenosis	XX (XX)	XX (XX)	XX
Intestinal obstruction	XX (XX)	XX (XX)	XX
Intestinal perforation	XX (XX)	XX (XX)	XX
Abdominal infection	XX (XX)	XX (XX)	XX
Bleeding	XX (XX)	XX (XX)	XX
Others†	XX (XX)	XX (XX)	XX
Stent or Tube-related complications, No. (%)	XX (XX)	XX (XX)	-
Stent displacement	XX (XX)	XX (XX)	-
Intestinal fistula‡	XX (XX)	XX (XX)	-
Mushroom-shaped tube-related dermatitis	XX (XX)	XX (XX)	-
Mushroom-shaped tube displacement	XX (XX)	XX (XX)	-
Stoma-related complications, No. (%)	XX (XX)	XX (XX)	-

Parastomal hernia	XX (XX)	XX (XX)	-
Dermatitis	XX (XX)	XX (XX)	-
Stoma obstruction	XX (XX)	XX (XX)	-
Stoma bleeding	XX (XX)	XX (XX)	-
Grade of complications			
I	XX (XX)	XX (XX)	XX
II	XX (XX)	XX (XX)	XX
III	XX (XX)	XX (XX)	XX
IV	XX (XX)	XX (XX)	XX
V§	XX (XX)	XX (XX)	XX
Converse to Stent-based Diverting Technique, No. (%)	-	XX (XX)	-
Converse to ileostomy, No. (%)	XX (XX)	-	-
Converse to salvage ileostomy, No. (%)	XX (XX)	-	-
Time of stent degradation			
No stent	XX (XX)	XX (XX)	-
Stent displacement	XX (XX)	XX (XX)	-
Before 3 weeks	XX (XX)	XX (XX)	-
3-4 weeks	XX (XX)	XX (XX)	-
5-6 weeks	XX (XX)	XX (XX)	-
Stoma ending, No. (%)#			
No stoma	XX (XX)	XX (XX)	-
Reversal on time (stage II)	XX (XX)	XX (XX)	-
Delayed reversal	XX (XX)	XX (XX)	-

Table 3

	Stent-based Diverting Technique	Ileostomy	P value
PHS and Costs	n=	n=	
Unplanned readmission, No. (%)	XX ± XX	XX ± XX	XX
PHS (stage I), days	XX ± XX	XX ± XX	XX
PHS (stage II), days	XX ± XX	XX ± XX	XX
PHS (Readmission),	XX ± XX	XX ± XX	XX
Total PHS, days*	XX ± XX	XX ± XX	XX
Total PHS (Only patients with reversal), days*	XX ± XX	XX ± XX	XX

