Research Institution: Sir Run Run Shaw Hospital, Zhejiang University

Register Number: NCT06204497

Date: 2025-10-06

Version: 1.1

1. Introduction

This trial is a multicenter, prospective, randomized, controlled, open label, parallel-group, non-inferiority trial to evaluate the safety and efficacy of stent-based diverting technique versus ileostomy in rectal cancer patients. In this trial, stent-based diverting technique is considered to reduce the overall length of post-operation hospital stay and medical costs, improve patients' quality of life, while not increasing the peri-operative complication rate. The primary endpoint is the incidence of severe complications within 90-day (Clavien-Dindo \geq III), and the secondary endpoints are the incidence of total complications, the incidence of anastomotic leakage (Grade B/C), and the postoperative hospital stays and cost, and the postoperative quality of life. Patients are randomly assigned into two groups in a 1:1 ratio: stent-based diverting technique receiving rectal cancer surgery followed by stent-based diverting technique, ileostomy group receiving rectal cancer surgery followed by ileostomy. The follow-up period finishes 90 days after the last patient is receiving the final surgery.

2. Population

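### Section 1, read naturally, ends follow-up 90 days after the last index operation, but the primary endpoint for stoma patients runs to 90 days after reversal, and no date fixes who counts as not reversed

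*SAP*

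**What the plan says.** Three places in SAP version 1.2 bear on when observation of the primary endpoint stops.

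- **Section 1 (Introduction), end of follow-up:** "Follow-up concluded 90 days after the last patient underwent surgery". The operation is not named.
- **Section 4.1 (Timing of Analysis), database lock:** "which will occur after all patients have completed the 90-day follow-up". Again no operation is named.
- **Section 4.6 (Primary outcome), the endpoint window:**
  - Control arm: "For the Control Group, from ileostomy creation to 90 days after stoma reversal".
  - SDT arm: "For the Study Group, from the SDT to 90 days after surgery", with the extension "if the patient undergoes ileostomy as a salvage procedure, the time frame will be extended to 90 days after stoma reversal".
  - Fallback, for patients in "both groups who do not undergo stoma reversal, the time frame will be defined as 90 days after the initial surgery". No date is given by which reversal must have happened for a patient to leave this group.

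In the Table 2 shell, the block labelled "Stoma ending, No" shows rows for no stoma, reversal on schedule and late reversal. No row for a stoma that was never reversed is visible.

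Superseded version 1.1, printed in the same file, has in its introduction: "The follow-up period finishes 90 days after the last patient is receiving the final surgery". That text no longer governs and is used here only as evidence of possible intent.

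**The concern.** Where version 1.2 uses *surgery* without qualification, it means the index operation. Section 4.6 sets 90 days after surgery apart from 90 days after reversal, and sections 2.4 and 4.4 speak of withdrawal before surgery. Read that way, section 1 closes follow-up three months after the last index operation, whereas section 4.6 requires a stoma patient to be observed for the time to reversal plus a further 90 days.

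Two things can then go wrong for late-enrolled stoma patients.

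1. A patient is reversed, but follow-up closes before 90 days have passed. Neither the reversal rule nor the fallback describes this patient.
2. A patient still awaiting reversal at closure looks the same as one who will never be reversed. The fallback would then cut the window to 90 days from the index operation.

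Whether an event is counted would depend partly on enrolment date, and two analysts following version 1.2 could classify the same patient differently. This concerns the primary endpoint of a test with a margin of 2.8 percentage points.

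**Working it through.** The SAP states no accrual length, time to reversal, sample size or event count, so there is no figure of its own to reproduce. The check compares the two windows and then sizes the gap under labelled assumptions.

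**Inputs.** From the SAP: follow-up closes 3 months (90 days) after the last operation (section 1); the control window ends 3 months after reversal (section 4.6); the margin is 2.8 points (section 4.6). Assumed: uniform accrual over A months; reversal T months after the index operation; a severe-complication risk q in the 90 days after reversal, spread evenly.

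**Step 1: who is incomplete, if index surgery is meant.** Let t be the months from a patient's index operation to the last index operation in the trial.

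- Observed: t + 3. Required: T + 3. The window is incomplete if t < T, so the share is T/A.
- Still unreversed at closure: t + 3 < T. This needs T > 3, and the share is (T − 3)/A.

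| A (months) | T (months) | Incomplete, T/A | Reversed but cut short | Unreversed at closure |
|---|---|---|---|---|
| 18 | 3 | 3/18 = 16.7% | 16.7% | 0% |
| 18 | 6 | 6/18 = 33.3% | 16.7% | 3/18 = 16.7% |
| 24 | 3 | 3/24 = 12.5% | 12.5% | 0% |
| 24 | 6 | 6/24 = 25.0% | 12.5% | 3/24 = 12.5% |

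Over a wider range (T from 60 to 180 days, A from 365 to 1095 days), the incomplete share runs from 60/1095 = 5.5% to 180/365 = 49.3%.

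**Step 2: who is incomplete, if the final operation is meant.** Every reversed patient has the full T + 3 months. The share is 0% for any A and T.

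**Step 3: possible effect on the control rate, index reading.** For T ≥ 3, unreversed patients lose the whole post-reversal window and cut-short patients lose half of it on average. The share of post-reversal time lost is (T − 3)/A + 0.5 × 3/A = (T − 1.5)/A.

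- T = 3, A = 24: 1.5/24 = 6.25%. With q = 2%, 0.0625 × 2 = 0.13 points.
- T = 6, A = 18: 4.5/18 = 25%. With q = 5%, 0.25 × 5 = 1.25 points.

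Over the wider range the understatement is about 0.04 to 1.85 points. This covers the post-reversal phase only. If the fallback is applied to unreversed patients, any event between day 90 and closure would be dropped as well.

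**Step 4: direction.** The risk difference is SDT minus ileostomy, and its upper bound is compared with 2.8 points. Lost control events raise the difference and work against non-inferiority. Lost events in SDT salvage patients lower it. SDT patients without a stoma have a complete window on either reading.

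**The case against.** The strongest reply is that this is loose drafting. Section 1 does not say which operation it means, version 1.1 referred to the final one, and the amendment summary records no change to follow-up. Section 4.1 makes lock conditional on every patient completing follow-up, which can be read as each patient's own section 4.6 window. On that reading sections 4.1 and 4.6 agree and only one sentence in section 1 is out of line. All of this stands, and it is why truncation can only be stated conditionally. It does not remove the conflict, because the governing text has no qualifier and its usage elsewhere points to the index operation.

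A reader might go further and infer the following, which the SAP does not support:

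- **That control patients were in fact cut short or misfiled.** No passage shows this. Misfiling also needs reversal later than 90 days after the index operation, and nothing says that patients awaiting reversal are placed in the fallback.
- **That partial windows are counted as complete without disclosure.** Section 4.2 removes patients with missing categorical outcomes from the denominator and promises to report the number included; section 2.2 requires adequate primary-outcome follow-up for the per-protocol population. Neither says how a partial window is classed. That is silence, not a rule to count it as complete.
- **That unreversed patients cannot be identified in the report.** The stoma rows in Table 2 carry a footnote mark whose text is not visible, and Table 3 has rows restricted to reversed patients.
- **That the problem favours SDT.** In the control arm it works the other way.

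**Conclusion.** The point holds as a contradiction about the primary endpoint window that should be fixed. On their natural readings sections 1 and 4.6 disagree, section 4.1 does not settle the matter, and no date separates a stoma not yet reversed from one never reversed.

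The size cannot be known from the SAP. The affected share of control patients is 0% if the final operation is meant. It is T/A if the index operation is meant, for example 12.5% to 33% under the assumed accrual and reversal times. The possible understatement of the control rate in that example is 0.13 to 1.25 points, on a further assumed risk of 2% to 5% after reversal. The control-arm effect is conservative for non-inferiority. The net effect is not guaranteed to be, because SDT salvage patients pull the other way.

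**What to change.** 1. **Align the texts.** Reword sections 1 and 4.1 so that follow-up and lock come only after each patient's own section 4.6 window has closed.
2. **Fix reversal status for analysis.** State a date by which a stoma is classified as not reversed, and apply the 90-day fallback only to patients in that class. This is a classification rule for the analysis, not a rule on when to reverse.
3. **If follow-up has already closed,** count every severe complication observed, including those in patients with incomplete windows. Treat only event-free patients with incomplete windows as having a missing outcome, with a sensitivity analysis, and report their number by arm.
4. **Do not let section 4.2 simply drop those patients.** Excluding event-free patients while keeping those with events inflates the rate, mostly in the control arm, which favours SDT. For illustration, suppose 14% of control patients have an observed event and a share s of the remaining 86% is dropped. The rate becomes 0.14/(0.14 + 0.86 × (1 − s)), which is 15.7% for s = 12.5% and 19.6% for s = 1/3. The plan should name a method that uses the follow-up these patients do have, and also show the result with them counted as event-free.
5. **Table 2.** Add a row *Not reversed at end of follow-up* to the stoma block.

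The cost is a few sentences and one table row, plus either a later lock or a disclosed count of incomplete windows. If nobody was truncated, that count is zero.

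### The as-treated rule in SAP section 2.3 does not exclude salvage ileostomy, so read literally it moves failures of delivered SDT, with their events, into the ileostomy group

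*SAP*

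**What the plan says.** SAP section 2.3 defines the as-treated population in two steps. First, it "comprises all randomized patients who actually received the intervention to which they were assigned, regardless of their original randomization group". Then it states that "participants randomized to the SDT group but who ultimately underwent ileostomy for various reasons were included in the ileostomy group in the as-treated analysis", and that the same applies in the other direction. The section closes: "All as-treated analyses were conducted as sensitivity analyses".

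Section 2.4 groups the safety population "based on the treatment actually received, on which safety monitoring was performed". It does not address patients who had both procedures.

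Two other places show that the plan knows salvage ileostomy as its own event:

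- Section 4.6, on the outcome window in the SDT arm: "if the patient undergoes ileostomy as a salvage procedure, the time frame will be extended to 90 days after stoma reversal".
- Appendix Table 2 has one row beginning "Converse to ileostomy, No" and another beginning "Converse to salvage ileostomy, No". Both are to be filled for the SDT arm and dashed for the ileostomy arm.

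Section 4.3 makes the as-treated analysis the place where treatment switching is explored. Section 4.8 has it repeat the primary model and compares ITT, per-protocol and as-treated results to judge whether protocol violations or missing data affect the outcomes.

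**The concern.** The sentence in section 2.3 can take in two different kinds of patient. One was converted to ileostomy at the index operation and never had SDT. The other had SDT and later needed an ileostomy as salvage. Moving the first to the ileostomy group is ordinary as-treated practice. Moving the second takes a patient who received SDT, along with any severe complication that followed it, and counts both against the control.

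The movement is one-way. An ileostomy patient has no corresponding salvage event, as the dash in Table 2 shows, so the reciprocal clause in section 2.3 offers no counterweight. Under section 4.6 the salvaged patient's window also runs from SDT to 90 days after stoma reversal, so every severe event in that period moves with the patient.

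At stake is the as-treated result as a check on the primary finding. If it credits SDT for SDT's own failures, agreement between ITT and as-treated is not evidence of robustness.

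A separate drafting fault sits in the same section. The first sentence admits only patients who received their assigned treatment, and the next reassigns those who did not.

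**Working it through.** **Inputs from the SAP**

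- Allocation 1:1 (section 1).
- Expected severe-complication rate with ileostomy 14%; margin 2.8 points on the risk difference (section 4.6).
- The as-treated analysis uses the same method as the primary analysis (section 4.8).

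**Assumptions, not in the SAP**

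- s = share of the SDT arm that has salvage ileostomy, varied from 1% to 5%.
- q = share of those salvaged patients with a severe event, set at 50% and 100%.
- Conversions at the index operation are left out, to isolate the effect of salvage.

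**The plan's own figure.** 0.14 × 0.2 = 0.028, so the margin reproduces. The corresponding ceiling for SDT is 14% + 2.8% = 16.8%.

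**Formulae.** Let pT and pC be the rates in the SDT and ileostomy arms as randomized. Under the literal rule:

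- as-treated SDT rate = (pT − s·q) / (1 − s)
- as-treated ileostomy rate = (pC + s·q) / (1 + s)

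Subtracting the as-randomized difference gives

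shift = −s(q − pT)/(1 − s) − s(q − pC)/(1 + s).

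The shift is therefore negative, in favour of SDT, whenever q exceeds both arm rates. Not every salvage need be a severe event for this to hold.

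**Worked case.** pT = pC = 0.14, s = 0.02, q = 1:

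- SDT: (0.14 − 0.02)/0.98 = 12.24%
- Ileostomy: (0.14 + 0.02)/1.02 = 15.69%
- Risk difference −3.44 points (from unrounded rates), where the true difference is 0.

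**Range of as-treated risk differences (points)**

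| Salvage share s | True RD 0 (14% v 14%), q = 50% | True RD 0, q = 100% | True RD +2.80 (16.8% v 14%), q = 50% | True RD +2.80, q = 100% |
|---|---|---|---|---|
| 1% | -0.72 | -1.72 | +2.11 | +1.11 |
| 2% | -1.44 | -3.44 | +1.42 | -0.58 |
| 3% | -2.16 | -5.16 | +0.72 | -2.28 |
| 5% | -3.61 | -8.62 | -0.66 | -5.67 |

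**Salvage share at which the shift equals the 2.8-point margin** (true rates equal): about 3.9% at q = 50%, 2.3% at q = 75% and 1.6% at q = 100%. Starting from 16.8% v 14% the figures are nearly the same: about 4.1%, 2.4% and 1.7%.

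**If salvaged patients stay in the SDT group**, salvage adds no shift: the as-treated difference is 0.00 in the first setting and +2.80 in the second.

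**The case against.** The strongest reply is that section 2.3 was meant for crossover only. It never uses the word salvage, although the SAP does so elsewhere when it means it. Its reciprocal clause fits two-way crossover: Table 2 has a conversion row for each arm but a salvage row for SDT alone. Section 4.3 speaks of crossover and treatment switching, and the amendment summary gives crossover data as the reason for adding the as-treated analysis. This stands as evidence of intent. A reader might infer that the plan definitely charges salvage cases to the control, and the text does not establish that. It does leave the rule unbounded, however, and nothing keeps salvage patients in SDT. Two programmers could build different as-treated sets in good faith.

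A reader might also infer that the safety population carries the same bias. Section 2.4 does not support this. It lacks the open-ended wording of section 2.3, and a patient given SDT and later salvaged did receive SDT. Section 2.4 is silent on patients who had both procedures; it does not misassign them.

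It is fair, too, that the sizes rest on s and q, which the SAP does not give. The larger figures need every salvaged patient to have a severe event, which the SAP does not say; at q = 50% the shift reaches the margin only near 4% salvage.

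Finally, the non-inferiority test is on ITT, per-protocol is a second sensitivity set that this rule does not touch, and no rule lets the as-treated result establish non-inferiority. All of that stands and limits the severity. The contradiction in the first sentence of section 2.3 is a genuine error, but it causes none of the computed shift.

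**Conclusion.** The point holds as a defect in the definition of a sensitivity population, and it should be fixed. Taken literally, section 2.3 includes salvage ileostomy after delivered SDT, and the as-treated risk difference then favours SDT whenever salvaged patients have an above-average severe-event rate. For assumed salvage of 1% to 5% with 14% in both arms, the shift is about -0.7 to -3.6 points (half with a severe event) or -1.7 to -8.6 points (all with one). A low single-figure percentage of salvage cases can therefore offset the whole margin.

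The documents do not support the further inference that the primary conclusion is compromised: section 4.3 keeps the ITT principle for it. The risk is indirect, namely that a comparison under section 4.8 is read as corroborating non-inferiority when the grouping itself produced the agreement. Confidence is high in the wording gap and in the direction under the stated condition. The size remains conditional on s and q.

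**What to change.** - **Section 2.3:** define the as-treated groups by the diversion created at the index operation. Only intraoperative conversions change group; patients given SDT who later have a salvage ileostomy stay in the SDT group with all their events.
- **Section 2.3, first sentence:** delete the words that tie the treatment received to the assigned one, so that it no longer contradicts the sentence after it.
- **Section 2.4:** state the same grouping rule for patients who had both procedures.

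This changes how patients are grouped for analysis and no clinical rule. The cost is a few lines of SAP wording and one grouping variable. Table 2 already reports conversion and salvage separately, so no new data are needed. The downside is that the as-treated results may look less favourable to SDT than under the literal rule.
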